#### **Primary Objectives and Secondary Objectives Involving Academic Outcomes:**

As is customary, our estimates are in standard deviations (SDs; effect sizes). We examined power assuming 20 schools, inclusion of 3-4 students per grade level across two grade levels (3.5 students per school), and randomization at the school level. The design targets on average 14 students per school, or 280 total. To allow for 15% loss to follow up at the student level, we assume 120 students per arm. Each student will have data collected at 4 time points: baseline, post-treatment, 5-month follow-up, and 12-month follow-up. For analysis, we will use all available data until the time of dropout. For power calculations, we assumed conservatively a baseline measure and one follow up per student.

We accounted for the reality that longitudinal measures at the student level increase power and clustering of students within schools decreases power. We assumed three relatively modest correlations of outcome measures within student over time: 0.5, 0.6 and 0.7, which correspond to SDs of change of 1.0, 0.8, and 0.6 for a 1 SD cross sectional difference. Correlations of 0.5 lead to no increase in power from the design, and correlations of 0.6 and 0.7 correspond to approximately 10% and 20% increases in power. To account for clustering, we assumed intra-cluster correlations (ICC)=0.01, typical in school-based trials (Office of Behavioral and Social Sciences Research, NIH: <http://esourceresearch.org/tabcid/384/Default.aspx>). We also used ICC=0.038. This ICC value corresponds to variation across schools on the order of 0.4 SD of the distribution of outcome scores, or the equivalent to a range of means across schools of 1.6 SDs, a modest degree of inter-cluster variation. The design effects of these assumptions are 1.03 (small) and 1.11 (modest), to be expected with a relatively small number of students per school, and correspond to a reduction in the effective sample size of 3-11%.

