[name] calculations were performed using PASS 11 (Hintze, 2011; [www.ncss.com](http://www.ncss.com)), which demonstrated 90% power to detect a change in outcomes equivalent to 0.5 or greater in cross-sectional SDs, assuming at least 12 students per school and model correlation of these scores within student over time (corr=0.7), and assuming an ICC of 0.038 (a relatively large degree of variation across schools). A change equivalent to 0.5 cross-sectional SDs in outcome scores and 12 students per school is still detectable (power>0.85) if the correlation within students over time is 0.7 and the ICC across schools is 0.038. Larger effects can be detected with greater power. These power estimates apply to both OTMP skills and academic outcomes using intervention as a binary outcome in an intent-to-treat analysis. Based on the pilot study of OST-S, we expected effect sizes for outcomes to be in the 0.6 to 0.8 range. These power calculations are likely conservative; inclusion of covariates might actually improve power.

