Linear mixed effects models were used to estimate the effects of OST-T2 on outcomes. Models had three levels: assessment time nested within student and students nested within school. All models included time (as splines), treatment, and time-by-treatment interactions. Mixed effects models included random intercepts for school (to account for clustering of students within schools), random slopes (over time) to allow for different trajectories across schools, and a random intercept and random slope for student to allow for variation in the effect of treatment assignment across students over time. Modeling for the clustering effect of schools accounted for more than one student being rated by multiple teachers; teachers rated a mean of 1.6 students and approximately 85% of teachers rated three or fewer students at each time point. Statistical significance was evaluated using a threshold p value of .0083, accounting for the estimation of three contrasts of time-by-treatment differences per outcome and two measures per domain (OTMP skills [COSS-P, COSS-T], homework performance [HPC, HPQ-T], and academic performance [ACES, APS]).

Mixed effects models facilitated both the graphic display, and contrasts, of curves depicting the expected values of outcomes over time from time zero until 12-month follow-up for the student with the last data collected. All confidence bounds reflected variances based on the multi-level linear model. To evaluate differences between conditions, we estimated model-based, expected values for outcomes at four preplanned times, 0 (baseline), 14 (post-treatment), 22 (5-month follow-up) and 55 (12-month follow-up) weeks, except for academic grades, which

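### The SAP's fixed .0083 for all six contrasts in a domain is valid, but Holm's step-down rule keeps the same 5% family-wise error and would add from 0 to about 10 points of power per contrast

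*SAP*

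**What the plan says.** The SAP (Data Management and Analysis) states: "Statistical significance was evaluated using a threshold p value of .0083, accounting for the estimation of three contrasts of time-by-treatment differences per outcome". The other factor in the divisor comes from the way outcomes are grouped, which the same sentence gives as "two measures per domain (OTMP skills [COSS-P, COSS-T], homework performance [HPC, HPQ-T], and academic performance [ACES, APS". The contrasts are changes from baseline estimated at fixed times: "0 (baseline), 14 (post-treatment), 22 (5-month follow-up) and 55 (12-month follow-up) weeks, except for academic grades". Grades are instead estimated at the start and the end of the school year. No step-down, hierarchical or other multiple-testing procedure is described.

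The protocol's power section (6.1.4) claims "90% power to detect a change in outcomes equivalent to 0.5 or greater in cross-sectional SDs", and then says that a 0.5 SD change "is still detectable (power>0.85) if the correlation within students over time is 0.7 and the ICC across schools is 0.038". It adds: "These power estimates apply to both OTMP skills and academic outcomes". It states no alpha and mentions no allowance for multiple contrasts.

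**The concern.** A single-step Bonferroni threshold holds every contrast to the strictest level, even after the others in the family have been rejected. Holm starts at the same .0083 and relaxes the threshold after each rejection, with the same family-wise guarantee. The protocol's primary objectives ask about efficacy at post-treatment, 5 months and 12 months, and OTMP skills are rated by both parent and teacher. Power for the individual contrasts therefore matters. A real but weaker effect, for example one that has faded by 12 months, could miss .0083 and yet be declared under Holm at no cost to the 5% target.

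**Working it through.** **Inputs.** From the SAP: threshold .0083, three contrasts, two measures per domain. From protocol 6.1.4: 0.5 SD, 90% or more than 85% power, 12 students per school, ICC 0.038, within-student correlation 0.5 to 0.7, stated design effect 1.11, and "we assume 120 students per arm". Assumed, because the documents do not give them: two-sided tests, family-wise 5%, and the correlations between the six test statistics (0 to 0.9 between times, 0 to 0.7 between measures).

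**1. Reproduce the threshold.** 0.05/(3 × 2) = 0.00833, which rounds to the stated .0083. With six independent true nulls, family-wise error is 1 − (1 − 0.0083)^6 = 0.0488.

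**2. Holm on the same family.** Order the six p-values and compare them with 0.05/6, 0.05/5, …, 0.05/1, that is .0083, .010, .0125, .0167, .025 and .05, stopping at the first failure. The first step is the Bonferroni threshold, so the chance of at least one rejection is identical, and everything Bonferroni rejects is also rejected by Holm.

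**3. Set the effect size.** 90% power at two-sided .05 means a mean z of 1.96 + 1.28 = 3.24. At .0083 (critical value 2.64) power is Φ(3.24 − 2.64) ≈ 72.6%. For 85% power, the mean z is 3.00 and power at .0083 is 64%.

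The 90% can be recovered with a change SD of 1.0 (correlation 0.5) and design effect 1 + 11 × 0.038 = 1.418. Then SE = √(2/120 × 1.418) = 0.154, 0.5/0.154 = 3.25, and power is 90.2% (86.8% using t on 18 df). These are not the inputs printed beside the claim, which are correlation 0.7 with a stated design effect of 1.11. Correlation 0.7 gives a change SD of √(2 × 0.3) = √0.6 = 0.775. With design effect 1.11 to 1.42 the mean z is then 4.75 to 4.20, and power at .05 is about 99%.

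**4. Compare the rules** by simulating six correlated z statistics (200,000 or more draws per setting). Power is averaged over the real effects. Ranges cover the assumed correlations and, in the last row, the design effects.

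| Scenario | Power at .0083 | Holm | Gain (points) |
|---|---|---|---|
| All six real, each 90% at .05 | 72.6% | 81–85% | 8.0–12.5 (10.0–10.7 at moderate correlations) |
| All six real, each 85% at .05 | 64% | 73–77% | 8.7–12.7 |
| Five of six real (90%) | 73% | 78–81% | 6–8 |
| Four of six | 73% | 77–78% | 4–6 |
| Three of six | 73% | 75–76% | 2–3 |
| Two of six | 73% | 74% | 1–2 |
| One of six | 73% | 73% | about 0 |
| All six at 0.6 SD, SE 0.154 | 90% | 95–96% | 5–6 |
| All six at 0.8 SD, SE 0.154 | 99.5% | 99.9% | 0.4 |
| All six at 0.5 SD, correlation 0.7 | 94–98% | 98% to over 99% | 1.3–4.5 |

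If the protocol's printed change SD of 0.6 is used as it stands with design effect 1.418, the mean z is 0.5/(0.6 × 0.1537) = 5.42. Power at .0083 is then Φ(2.78) = 99.7%, so at most 0.3 points remain to be gained.

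The gain falls mainly on the weaker contrasts. With mean z of 4, 3 and 2 at the three times for both measures, it is about 2, 9 and 16 points.

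**5. Error rates.** With all six null, family-wise error is identical under the two rules. With three of six null, it is about 1.7–2.4% for Bonferroni and 2.7–4.2% for Holm, both below 5%.

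**The case against.** The SAP's rule is valid, simple and conservative, and its intervals match its decisions. Preferring Holm is advice about efficiency. That stands, and it limits how strongly the point can be put. Four stronger readings are tempting, and the documents do not support them.

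- **A flat loss of about 10 points.** This requires all six effects to be real and each to have roughly 85–90% power at .05. Section 6.1.4 expects effects of 0.6 to 0.8 SD from the pilot and uses a correlation of 0.7. Either assumption shrinks the gain. So does an effect seen by one rater only, a pattern that protocol section 1.4 reports for a related school programme.
- **Nothing is bought by the stricter rule.** That is true only against the 5% target. Bonferroni's actual error is lower when some effects are real. It also bounds the expected number of false rejections at 0.05, which Holm does not (0.052–0.057 in simulation with all six null).
- **The trial needs all six contrasts.** Under the 90% scenario, all six are significant in 30–44% of draws at .0083 and 61–70% under Holm. However, no success rule in either document requires all six. If one did, each contrast could be tested at the full alpha and neither procedure would be needed.
- **Academic grades were wrongly tested at .0083.** The SAP explains the threshold by three two-measure domains, and grades are in none of them. It does not say which threshold grades received. This is an ambiguity to clarify, not an established fault.

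The timing objection also stands. The SAP is written in the past tense and already reports weighted balance results and 12-month medication rates, so a change now may come after the outcome analyses.

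**Conclusion.** The point holds as a modest, nearly free improvement. The fixed .0083 is a correct Bonferroni threshold, and Holm dominates it at the same family-wise 5% whatever the correlation. The average gain per real contrast runs from about 0 to about 10 points, and up to 12.5 if the six statistics were independent. The top of that range belongs to the planning alternative with all six effects real. On the protocol's own expected effects or its correlation of 0.7, the gain is about 0 to 6 points. Power to find at least one effect in a domain is unchanged. That Holm never rejects less, and its 5% bound, do not depend on the assumed correlations; the power figures do, and they also assume two-sided tests and a family-wise 5%.

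**What to change.** Within each of the three two-measure domains, report Holm-adjusted p-values for the six contrasts at family-wise 5%, next to the results at .0083. If outcome data have already been analysed, label the Holm results post hoc and keep the .0083 results as the specified analysis. Because Bonferroni's rejections are a subset of Holm's, choosing between these two rules late cannot raise within-domain family-wise error above 5%.

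Keep the Bonferroni intervals for display, and note that an interval may include zero for a contrast that Holm rejects. State which threshold applied to academic grades.

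The cost is a short SAP addition, one extra column of p-values and the post hoc label. No new data or models are needed.

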### 2.1 Primary Objectives (or Aims)

The primary objectives of this study are:

- Determine the efficacy of OST-S with regard to improving **proximal student outcomes** (OTMP skills, academic self-efficacy) relative to a treatment as usual control group (TAU) at post-treatment, as well as 5-month and 12-month follow-up.
- Determine the efficacy of OST-S with regard to improving **distal student outcomes** (academic productivity and grades) relative to TAU at post-treatment, as well as 5-month and 12-month follow up.

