### 6.1.3 Secondary Endpoints

The secondary endpoints are student academic productivity, homework, and academic grades.

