## 6.2 Preliminary Analysis to Respond to Project Officer

### 6.2.1 Goals of Preliminary Analyses

Our study team has identified three primary goals to address the question of whether OST-S is having its intended effect to address the request of the project officer. The goals of the preliminary analyses are contained within the original study aims and do not represent new aims.

1. **Determine whether OST-S may be effective in improving proximal outcomes (students' organization, time management, and planning [OTMP] skills) relative to a treatment as usual, waitlist control group (TAU-WL) at post-treatment.**

This goal is included within study Aim 1. We will examine only the primary study outcome, students' OTMP skills, assessed by parent and teacher ratings on the Children's Organizational Skills Scale (COSS-P, COSS-T), and we will examine outcomes only at post-treatment (not follow-up).

**2. Determine whether there may be a differential effect of OST-S on OTMP skills as a function of student grade level (3rd to 5th grade).**

This goal was included as an original study aim. It is especially important to examine this goal because there is good reason to believe 3rd graders may not respond as well to OST-S as older students. It is also important to examine this goal because by chance (due to randomization) the year impacted by COVID included mostly 4th and 5th graders, whereas the years before this included more younger students. Therefore, our sample of 175, which was designed to be evenly distributed across the grades, currently underrepresents 5th graders (Grade 3 –  $n = 64$ ; Grade 4 –  $n = 72$ ; Grade 5 –  $n = 39$ ).

**3. Determine whether there may be a differential effect of OST-S on OTMP skills as a function of the resource level of schools (low, middle, or high subsidized lunch rate).** This goal was included as an original study aim. It is important to examine this goal because prior research has suggested that schools with fewer resources (high subsidized lunch rates) might not do as well in implementing such interventions given the multiple stressors their staff face. That being said, fidelity implementation data suggests that our school partners generally are implementing the intervention with high quality regardless of school subsidized lunch rate.

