were estimated for beginning and end of school year. Those actual times were translated into their equivalent values in the models for restricted cubic splines. Expected values were then the product of these times and estimated coefficients from the mixed effects models. The primary overall estimate of intervention effect for each outcome was the between-group difference of the change in expected values (means) from time zero to the prespecified outcome assessment times. The mixed effects models applied in this study assume that missing scores were missing at random, a reasonable assumption given that we also adjusted for student baseline covariates that might explain missed assessments. Analyses used all available scores, consistent with an ITT approach. Sensitivity analyses were conducted to determine whether data collected after the school shutdown due to the COVID-19 pandemic (March 16, 2020) altered study findings.

Mixed effects models were also used to estimate student-level outcomes at each assessment time. We estimated random effects for students and schools to determine model-based estimates, which reflect expected values (average score of the entire group) plus individual random effects (departures of the individuals from average). Statistical theory suggests that model-based predictions provide better estimates of true values than the actual data. Model-based predictions, called “empirical Bayes” estimates, combine individual measures with group-level expected values in a manner that permits individual estimates to derive strength from the group effects (Efron & Morris, 1973). Using these estimates for each student at each assessment point, we categorized all students based on thresholds derived from normative data sets or common-sense scale values on measures. For the COSS-P, COSS-T, HPC, and HPQ-T, thresholds were set at one-half standard deviation below/above the mean of the normative sample to indicate performance within the normal range (for normative information, see masked for review; [name] et al., 2006; [name] et al., 2007), as this corresponds with a medium effect size. For the ACES and APS, threshold values were set at a value reflecting performance at the standard for grade level (3.0) or above. For academic grades, the threshold was set at a value of 3.0 or above.

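### The SAP's .0083 threshold holds error near 5% within one outcome domain but is applied in three, with grades uncounted, and the SAP does not carry over the protocol's ranking of primary and secondary endpoints.

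*SAP*

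**What the plan says.** The SAP (Data Management and Analysis) sets one threshold for every contrast: "Statistical significance was evaluated using a threshold p value of .0083". The reason it gives for that figure is that it is "accounting for the estimation of three contrasts of time-by-treatment differences per outcome and two measures per domain". It lists the domains as "OTMP skills [COSS-P, COSS-T], homework performance [HPC, HPQ-T], and academic performance [ACES, APS". Grades are also modelled, but "were estimated for beginning and end of school year"; they belong to none of the three domains, and no threshold is stated for them. The SAP uses the word primary for an effect estimate, not for an outcome: "The primary overall estimate of intervention effect for each outcome was the between-group difference of the change in expected values (means"). It does not mention academic self-efficacy.

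The protocol ranks outcomes in four places:

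- Section 2.1 lists two primary objectives. One covers the proximal outcomes (OTMP skills, self-efficacy). The other covers distal outcomes: "academic productivity and grades) relative to TAU at post-treatment, as well as 5-month and 12-month follow up".
- Section 6.1.2 makes OTMP skills and academic self-efficacy the primary endpoints, at post-treatment, 5 months and 12 months.
- Section 6.1.3 says: "The secondary endpoints are student academic productivity, homework, and academic grades".
- Section 6.2.1 says of the preliminary analysis: "We will examine only the primary study outcome", by which it means OTMP skills alone, rated by parents and teachers.

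**The concern.** A threshold of .0083 looks like full protection against multiple testing, but its divisor leaves out the number of domains. Three domains each held near 5% do not give 5% for the trial, unless one of them is designated to decide it. The SAP designates none.

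The gap matters most if the domains disagree. Suppose no OTMP contrast is significant and one ACES contrast has p below .0083. Under protocol 2.1, read as covering that measure, a primary objective has been met. Under 6.1.3 the result is secondary. The SAP does not choose between them, so the meaning of a positive trial is left to whoever writes the report.

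**Working it through.** **Inputs from the documents**

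- Threshold per contrast: .0083 (SAP).
- Contrasts per outcome: 3 (SAP; weeks 14, 22 and 55, each compared with time zero).
- Measures per domain: 2, in 3 named domains (SAP).
- Grades: at least 1 further contrast, from beginning to end of school year (SAP).
- Self-efficacy: one measure, the PALS subscale, at three follow-ups (protocol Table 1 and 6.1.2).

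**Inputs assumed**

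- An overall two-sided level of 0.05. The SAP does not state it, but the threshold implies it.
- Correlations between the test statistics. The documents do not give these. The within-student correlations of 0.5 to 0.7 in protocol 6.1.4 are only a rough guide to the correlation between time points, and say nothing about raters or domains.

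**Step 1. Reproduce the threshold.** 0.05 / (3 × 2) = 0.00833, which rounds to .0083. The divisor is therefore the six contrasts of one domain.

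**Step 2. Error within one domain.** The Bonferroni bound is 6 × .0083 = .0498. If the tests are independent, 1 − (1 − .0083)^6 = 4.9%. With a common correlation of 0.7 it falls to about 3.3%. The threshold does what it says inside a domain.

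**Step 3. Error across three domains.** There are 3 × 6 = 18 contrasts. The bound is 18 × .0083 = 14.9%. If independent, 1 − (1 − .0083)^18 = 13.9%. Simulating 18 two-sided normal tests at .0083, with no true effect anywhere and one common correlation, gives:

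| Common correlation | Chance of at least one false positive |
|---|---|
| 0 | 13.9% |
| 0.3 | about 11.9% |
| 0.5 | about 9.5% |
| 0.7 | about 6.5% |

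Separate correlations for time (0 to 0.8), for measures within a domain (0 to 0.7) and across domains (0 to 0.5) give 8.2% to 13.9%.

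**Step 4. Add grades.** One grades contrast at .0083 makes 19 tests: 1 − (1 − .0083)^19 = 14.6% if independent, with a bound of 19 × .0083 = 15.8%.

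**Step 5. Apply the protocol's own ranking.** If OTMP skills are the only primary domain, Step 2 applies and .0083 needs no change. If self-efficacy stays co-primary, the primary family has 6 + 3 = 9 contrasts. At .0083 the bound would be 9 × .0083 = 7.5%, so the divisor becomes nine: 0.05 / 9 = .0056.

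**The case against.** The strongest reply is that the protocol already settles the matter. Section 6.1.2, under a heading that says primary endpoint, names OTMP skills and self-efficacy; 6.1.3 makes the rest secondary; and 6.2.2 calls the three OTMP goals of the preliminary analysis the most important aims. The SAP's silence does not cancel this. The SAP is also open about what .0083 covers and nowhere promises 5% for the whole trial. Controlling error separately for each stated objective is a choice on which statisticians differ.

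Much of this stands. A reader might infer that the documents contain no hierarchy and that 18 contrasts were planned with equal standing. They do not support that: 6.1.2 and 6.1.3 give an explicit ranking. A reader might also infer that the trial's false-positive rate is simply 9% to 14%. That range omits the 6.5% case at correlation 0.7. It also needs a global null and a rule that any hit counts as efficacy, and no passage states such a rule.

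The reply does not remove two things. Protocol 2.1 places productivity and grades among the primary objectives, so the ranking is contradicted inside the protocol itself. And the SAP, which governs the tests, neither adopts the ranking nor mentions self-efficacy nor says how grades are to be judged.

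**Conclusion.** The point holds as a failure to carry over and reconcile the hierarchy. The estimates themselves are unaffected. What is unsettled is which results may be called evidence of efficacy, and at what error rate.

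If a significant result in any of the three domains counts, the chance of at least one false claim is about 6.5% to 14% over common correlations of 0.7 down to 0. This assumes no effect in any domain, and grades add a little. If the ranking in 6.1.2 and 6.1.3 governs, the OTMP domain is already held at or below 5% by the threshold in use.

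It would also be tempting to conclude that a formal gate, passing alpha from OTMP to the other domains, is required. It is not: labelling the other domains as secondary is enough. Moreover, the SAP is written in the past tense and already reports trial data (medication rates to 12 months, covariate balance after weighting), so a gate added to it now could not supply prespecified confirmatory control.

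**What to change.** In the SAP:

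- Name OTMP skills (COSS-P and COSS-T) as the primary domain to which .0083 applies.
- State the status of the self-efficacy endpoint in protocol 6.1.2. If it stays co-primary, count its three contrasts and use 0.05/9 (.0056) for the primary family. If it does not, say so and amend 6.1.2.
- Label homework, academic performance and grades as secondary, reported as supportive estimates with confidence intervals and not as stand-alone evidence of efficacy.
- Disclose that the ranking was written into the SAP late and that it follows protocol 6.1.2 and 6.1.3.

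In the protocol, move the distal objective in 2.1 to the secondary objectives, to match 6.1.3.

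This changes wording only; no model or data collection is affected. The costs are that a significant homework, academic or grades contrast could not by itself support an efficacy claim, and that the primary threshold becomes somewhat stricter (.0056 in place of .0083) if self-efficacy stays co-primary.
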